## 7. VISITS AND ASSESSMENTS:

### 7.1. Scheduled of visits and assessments (APPENDIX III)

#### 7.2. Assessments for visits:

- Preanesthesia visit:
  - Clinical evaluation
  - ASA (American Society of Anesthesiologists) classification
- Selection visit (Day -1):
  - Informed consent form,
  - Preoperative clinical data (demographic data, previous diseases/medication).
- Day of the surgery visit (Day 0).
  - Hemodynamic data (EV1000).
  - Arterial and venous gasometry. In anesthetic induction, after 20 minutes of the onset of one lung ventilation and at the end of the surgery.
  - Adverse events
- 4 hours after surgery - visit (Day 0):
  - Laboratory test (creatinine, PCR)
  - Arterial and venous gasometry, hemodynamic data (EV1000).
  - Adverse events
- 24 hours after surgery - visit (Day 1):
  - Laboratory test (creatinine, PCR)
  - Arterial and venous gasometry, hemodynamic data (EV1000).
  - Adverse events
- 48 hours after surgery - visit (Day 2):
  - Laboratory test (creatinine, PCR)
  - Adverse events

- 72 hours after surgery - visit (Day 3):
  - Laboratory test (creatinine, PCR)
  - Adverse events
- 1 month after surgery - visit:
  - Adverse events
  - Survival

## **8. EFFICACY ASSESSMENT:**

### **8.1. Efficacy assessment:**

This evaluation will be made to all randomized patients:

- Hemodynamic control of the cardiac index.
- Incidence of acute renal failure.
- Incidence of acute respiratory distress syndrome, pneumonia, need for invasive or non-invasive mechanical ventilation.
- Incidence of postoperative nausea and vomiting.
- Incidence of atrial fibrillation.

### **8.2. Laboratory tests**

The laboratory tests will be carried out in the local laboratories of H. U. Virgen del Rocio to measure the parameters mentioned below, which can be done more frequently if necessary. The gasometries will also be performed in the operating room gasometers. The determinations will include, at least, the following biochemical parameters:

- Creatinine, PCR.
- Arterial gasometry: Hemoglobine, lactate, PaO2, Hb, pH.
- Venous gasometry: Central venous oxygen saturation.

## 9. **SAFETY ASSESSMENT**

### 9.1. Methods for the evaluation of safety

Safety will be assessed in all patients participating in the study, which is by intention to treat (ITT). All adverse events (AE) occurring since the informed consent is signed until the final visit will be collected.

### 9.2. Definitions

Adverse Event (AE): Is any incidence detrimental to health in a patient or subject of a clinical trial treated with a drug, even if it does not necessarily have a relationship with such treatment. An AE can therefore be any unfavourable sign and unintended (including an abnormal laboratory finding), symptom, or disease temporarily associated with the use of a medication in research, whether or not it is related to the investigational medicinal product.

Adverse reaction (AR): is considered to be any harmful and unintended reaction to a research drug, irrespective of the dose administered. Unlike an AA, in the case of an RA there is a suspicion of a causal relationship between the investigational drug and the AE.

Imputability Criteria: the promoter will classify AA, based on their causal relationship with the drug, according to the Algorithm of Karch and Lasagna (1977), as:

Definite: There is a reasonable temporal sequence between the administration of drug and the appearance of AA. This event coincides with the AR described for the drug, improves with suppression or reappears after its readministration and cannot be explained by alternative causes.

Probable: there is a reasonable temporal sequence between the administration of drug and the appearance of AA. This event coincides with the AR described for the drug, improves after discontinuation of treatment and cannot be explained by other alternatives.

Possible: there is a reasonable time sequence between the administration of the drug and the appearance of AA. This event coincides with the AR described for the drug but can be explained by alternative causes.

Conditional or improbable: there is a reasonable time sequence between the administration of the drug and the appearance of AA. This event does not coincide with the RAs described for the drug and can be explained by alternative causes.

Not Related: there is no reasonable time sequence between the administration of the drug and the appearance of AA. This event does not coincide with the AR described for the drug and can be explained by alternative causes.

For the purposes of expeditious notification, the categories: definitive, probable and possible of

the algorithm of Karch and Lasagna (1977) will be considered as related and the conditional or unlikely category of said algorithm will be considered as unrelated.

The determination of the possible relationship with the treatment of the study is a responsibility of the principal investigator of the research centre or of the person designated by the latter.

Seriousness. Is considered severe any AE or AR that at any dose:

- Cause the death of the patient
- Threatens the life of the patient
- Require hospitalization or prolongation of patient hospitalization
- Cause disability or permanent or major disability
- It results in a congenital anomaly or malformation

For the purposes of notification, suspicions of AA or AR that are considered to be medically important, but not meet the above criteria, including medical events that require intervention to prevent any of the consequences described above, will also be notified as serious. All suspicions of transmission of an infectious agent through a medicine will also be considered serious.

Do not confuse the concept of "serious", described previously, with "severe" that refers to the intensity of AA or AR (mild / moderate / severe).

#### Serious and Unexpected Adverse Reaction (SUSAR)

Any serious AR whose nature, intensity or consequences do not correspond with the reference information for the drug. In this study, baseline information for the drugs being studied will be the technical file. The unexpected nature of an AR is based on the fact that it has not been observed previously and will not be based on what could be anticipated based on the Pharmacological properties of the medicinal product.

### 9.3. Adverse events management

#### 9.3.1. Adverse events/pregnancy recording

Crucial data related to the AE are to be included on a specific form provided for the study. In order to collect all the information related to possible AE in the study, each study team will be trained during the site initiation visit on the definitions and rules for communication of an AE. Any AE, whether it is connected to the study medication or not, has to be recorded in the CRF which contains a specific pharmacovigilance section. Serious adverse events must be completed with more detailed information including the event description (according to international guidelines in pharmacovigilance), date of onset

and resolution, severity, assessment of causality to study medication, action taken and other concomitant medication/procedures used for the treatment of the AE. Any AE occurring is monitored using initial and follow-up communication until resolution.

The severe adverse event (SAE) form is centralized in the CTU and its personnel is responsible for reception (by fax or e-mail communication), registration and resolution of queries with participating sites. The identification of any SUSAR is assessed by a safety medical monitor in order to evaluate if information is to be communicated to Regulatory Authorities, Ethics Committees and Investigators following Good Clinical Practice (GCP) rules. In such a case, communication through the EudraVigilance system is foreseen. The safety medical monitor is responsible for any updates in safety information on the investigational medicinal product (IMP).

AA will be collected since the patient signs Informed Consent (CI) up to 28 days after administration of the last dose of the drug in investigation and/or last visit. All AA/pregnancy should be documented in the clinical history of the patient and in the CRF. All AAs should be monitored until their resolution, or at least during the 30 days after discontinuation of study drugs (whatever occurs first), until the toxicity returns to a degree  $\leq 1$ , or until the toxicity is considered irreversible. In the case of collecting a case of pregnancy information will be collected on:

1. Normal birth, spontaneous or therapeutic abortion (any anomaly congenital detected in the aborted fetus must be documented), dead, congenital anomaly.
2. Neonatal deaths occurring within 30 days of birth.
3. Death of an infant after 30 days if the investigator suspects that he is related to intrauterine exposure to study medication.
4. All infants born after fetal exposure should be followed during the first 12 months after delivery.

Lack of efficacy and overdose should be considered as AA and be collected as such in the CRF. Any exacerbation of a pre-existing disease occurring after initiation of treatment of the study is also considered as an AA. Any abnormal results in the laboratory tests that the investigator considers clinically significant and requiring a dose adjustment of the treatment, the transient or permanent interruption of such treatment, or any other type of intervention or diagnostic evaluation to assess the risk associated with patient, will be collected as AA, and should be investigated and monitored adequately.

### 9.3.2. Adverse effects due to non-investigational medicinal products

NIMPs are "non-investigational medicinal products (IMPs)" referred in Article 2(d) of Directive 2001/20/EC, which may be provided to patients participating in a clinical trial according to the protocol.

For example, some clinical trial protocols require the use of pharmaceutical specialties as concomitant treatments or rescue due to prophylactic, diagnostic or therapeutic reasons and/or for ensure that subjects receive adequate medical care. They may also be used, according to the protocol, to induce a physiological response. These pharmaceutical specialties are not considered research drugs (IMP) according to Directive 2001/20/EC and PCB standards and are classified as "noninvestigational medicinal products" (NIMP). Any AA that may result from the administration of a NIMP should be collected in the CRF. If an SAE is considered to be related only to the NIMP and not relevant to the safety of the study, the investigator is obliged to communicate it, by Yellow Card, to the Pharmacovigilance Centre.

#### Procedure for notification of SAE/pregnancies (appendix I)

In the event of an SAE or a pregnancy case is collected, a member of the investigating team will complete and sign the notification form and will send it, by fax, immediately and always within 24 hours after having knowledge of the event to: [contact].

The CTU staff will review the form received and, if necessary, will request additional information from the investigator. When additional information is obtained, or it is resolved or unlikely to change, a follow-up report must be completed and faxed to the CTU. If there is a suspicion of a SUSAR, the investigator must provide the follow-up information requested by the CTU. Any SAE occurring more than 30 days after the end of treatment (without a time limit) should be reported if the investigator considers AAG to be related to the study treatment (i.e, if it is a serious adverse reaction) or if it is medically important.

It is not necessary to notify the CTU of the following SAE:

- Hospitalization or death due to the progression of haematological disease.
- Hospitalization for the performance of scheduled tests.
- Hospitalization to administer the study drug or to provide palliative care, terminal care or to perform scheduled surgical interventions.
- Hospitalization or prolongation of hospitalization to perform a procedure required by the protocol.
- Hospitalization or prolongation of hospitalization as a part of the routine procedure of the centre (for example, removal of a stent after surgery)

They will be collected in the CRF and in the patient's medical history.

Expedited notification of SUSARS to Health Authorities: The CTU will be responsible for notifying all the SUSARS collected in the study to the AEMPS, to the CEICs and to the Health Authorities, following the procedure indicated in the current legislation.

#### 9.3.3. Notification deadlines

The maximum period for notification of an individual SUSAR suspect case shall be 15 calendar days from the date on which the promoter has had knowledge of it. When SUSAR is suspected of causing death the patient, or endangered his life, the promoter will send the information within 7 calendar days from the date on which he/she become aware of it.

#### 9.3.4. Expedited notification of any other relevant safety information

The CTU will also notify, in an expeditious manner, all information that could modify the benefit/risk balance of the investigational medicinal product, or determine changes in the administration schedule or in the performance of the trial.

#### 9.3.5. Annual safety reports

Safety annual reports are issued with all the safety information in the study being reported to regulatory Authorities and Ethics Committees.

#### 9.3.6. Notification to investigators

The CTU will communicate to the investigators any safety information that may affect the safety of the trial subjects as soon as possible. The SUSAR information will be sent annually, in an aggregated form, in a list along with a brief analysis of the data provided. Throughout the study, the investigator will also be informed of any safety aspects that impact the conduct of the clinical trial or product development, including interruption of the development program or modifications to the protocol related to safety.

#### 9.4. Discontinuation of study drugs due to adverse events.

Certain events or conditions may necessitate temporary or permanent discontinuation of study medication. Patients presenting such events or conditions will remain in the study and will be followed until completion. Any patient who interrupts the study medication should temporarily restart it as soon as possible.

Study procedures will be discontinued and will be replaced by out-of-study procedures with continuing the follow-up of patients. If the administered drug is permanently discontinued, subsequent therapy is left to the discretion of the investigator.

#### Temporary discontinuation

Criteria for temporary discontinuation of study drugs: The development of a toxicity that, depending on its nature and severity, requires a temporary discontinuation of study medication until the toxicity is resolved, as well as the development of another medical condition that would discourage the

administration of study drug. The decision to temporarily interrupt study medication in this situation will be left to the discretion of the investigator. The period during which patient is not taking the study medication will be as short as possible.

#### Permanent discontinuation

Criteria for permanent discontinuation of study drugs: Toxicity development requiring permanent discontinuation of any study drug, patient refusal to continue treatment, when in the opinion of the investigator continuing study therapy is not the best option for the patient and completion of the study.

## **10. STATISTICAL ANALYSES**

### **10.1. Sample size:**

With respect to the calculation of the sample size, we do not have data from previous studies or bibliography from any similar study that can be used to calculate the sample of our study, so we will carry out a pilot study (30 patients, 15 in each group). As it was mentioned before, the primary aim of this study is to quantify and compare the percentage of the intraoperative time in which the cardiac index is equal or superior to 2.2 l/min/m^2 in patients who receive either goal-directed therapy or standard hemodynamic management in lung resection surgery.

### **10.2. Statistical methods**

Normality of the data will be assessed using the Kolmogorov-Smirnov test. A descriptive analysis expressing qualitative variables as proportions and quantitative variables as mean (SD) or median and interquartile range (RIC), depending on if they follow a normal distribution or not, will be performed. In order to compare study groups, the Chi squared test or Fisher's exact test for qualitative variables and t Student's test or Mann-Whitney U, when necessary, in quantitative variables will be used. Analysis will be performed using the Statistical Package for Social Sciences (SPSS Inc, Chicago III, U.S.A.) v 19.0.

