## 5. CLINICAL TRIAL DESIGN

### 5.1. Outcome measures

#### Primary outcome measures:

- Percentage of the intraoperative time in which the cardiac index is equal or superior to 2.2 l/min/m^2 (%) [Time Frame: During the total duration of the surgery].

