## 5.2. Randomization

The sampling method will be non-probability consecutive sampling. Randomization was conducted using random numbers obtained from statistical analysis tool EPIDAT (Epidat: Version 4.2, July 2016. Consellería de Sanidade, Xunta de Galicia, España; Organización Panamericana de la Salud (OPS-OMS); Universidad CES, Colombia. Available at: <http://www.sergas.es/Saude-publica/EPIDAT>). Patients will be recruited the day before the surgery, they will be informed about the trial and informed consent will be obtained. To prevent bias, randomization list will be guarded by the clinical trial unit. The anesthesiologist will call the clinical trial unit to obtain the randomization sequence when a patient is selected and the arterial line is placed.

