### Anesthetic protocol

1. Basic Anesthetic Monitoring: EKG, BP, SpO2.
2. Placement of peripheral venous line on the opposite arm of the surgery. 16 gauge if possible.
3. Administration of midazolam 2 mg IV if necessary.
4. Thoracic epidural catheter placement: T2-T6.
5. Biespectral index sensor placement.
6. Placement of **TOF-Watch** monitoring.

7. Induction:
  - Fentanyl 2 mcg/Kg IV.
  - Propofol 2 mg/Kg IV.
  - Rocuronium 0,6 mg/Kg, after calibration of TOF-Watch monitor.
8. Orotracheal intubation. Comprobatation of correct placement of double lumen endotracheal tube with flexible bronchoscopy. Bladder catheterization.
9. Mechanical Ventilation, volume control. Tidal volume 8 ml/kg ideal weight, respiratory rate 12-14 breaths per minute. FiO2 40% and positive end-expiratory pressure 5 cm H2O.
10. Sevoflurane for maintenance of general anesthesia, BIS objective between 40 and 60.
11. **Antibiotic prophylaxis** (Cefazolin 2g IV). We repeat cefazolin 2 g three hours after the beginning of the surgery.
12. Placement of an arterial line on the radial artery of the opposite arm of the surgery. Invasive arterial blood pressure monitoring (FloTrac system). Obtaining baseline VSI and CI value. ARTERIAL BLOOD GAS SAMPLING (induction) AND LABORATORY BLOOD TEST (creatinine), ev1000 clinical platform (hemodynamic data collection).
13. **RANDOMIZATION (trial treatment)**, Clinical Trial Unit, HUVR.
14. Central venous catheterization of the internal jugular or subclavian vein of the side of the surgery. VENOUS BLOOD GAS SAMPLING (induction).
15. Placement in lateral decubitus position. Inflation of the bronchial balloon of the double lumen tube after verification with fiberoptic bronchoscopy. Placement of thermal blanket.
16. Alveolar recruitment maneuver in bipulmonary ventilation: With pressure controlled ventilation, we set the inspiratory time at 50%, and we establish the respiratory rate at 12 rpm. The pressure over PEEP (Positive End-Expiratory Pressure) is kept constant at 20 cm H2O. The inspiratory pressure and the PEEP increase simultaneously and progressively from 30/10 to 35/15 and finally to 40/20 cmH2O. This last 40/20 cmH2O recruitment pressure is maintained for 10 cycles. Subsequently, the PEEP decreases gradually, returning to the baseline parameters, maintaining the PEEP at 7 cmH2O. After performing the recruitment maneuver, we return to volume controlled ventilation.

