17. Begin unipulmonar ventilation. VT 4-6 ml / kg ideal weight. Start FiO2 at 80%, and progressively reduce to 50%, once stable SpO2 above 90% is achieved. PEEP 7 cm H2O. Respiratory rate that avoids auto-PEEP and aiming at PaCO2 values between 40 and 60 mm Hg (permissive hypercapnia). Airway peak pressures below 30 cm H2O. Alveolar recruitment in unipulmonar ventilation if necessary.
18. Epidural bolus of 5-7 ml of bupivacaine 0.1% plus fentanyl 5 mcg/ml.

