**19. START OF SURGERY.**

20. ARTERIAL AND VENOUS BLOOD GAS SAMPLING (OLV-20 min). ev1000 clinical platform (hemodynamic data collection)

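### Section 10.2 leaves the primary comparison to an unadjusted test chosen by a normality check, plans no between-arm estimate with an interval, and does not use the cardiac index recorded before randomisation

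*Combined protocol and SAP*

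**What the plan says.** Section 10.2 does not mention the primary outcome by name, so its general rule for quantitative variables applies. Normality is checked with Kolmogorov-Smirnov, and each arm is described by mean (SD) or median and interquartile range accordingly. The arms are compared by Student's t or "Mann-Whitney U, when necessary, in quantitative variables will be used". Section 10.4 adds only the ITT and per-protocol populations. No section plans a between-arm difference, a confidence interval, a covariate or a model.

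Sections 4 and 10.1 both state that the primary aim is to quantify and to compare the outcome. Section 10.1 sets 30 patients, 15 per arm, and says that no earlier data exist for a sample size calculation.

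Baseline cardiac index is available in time. Step 12 of the anesthetic protocol (section 5.3) includes "Obtaining baseline VSI and CI value", and step 13 is "RANDOMIZATION (trial treatment)". Section 5.2 agrees: "The anesthesiologist will call the clinical trial unit to obtain the randomization sequence when a patient is selected and the arterial line is placed". It describes no stratification or balancing on cardiac index. Appendix III schedules cardiac index at induction without distinguishing the arms. The outcome window in section 5.1 is "During the total duration of the surgery".

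**The concern.** A pilot without planning data has one main product: an estimate of the difference and an honest statement of its uncertainty. As written, the plan guarantees a p-value and per-arm summaries. Which comparison accompanies them depends on a normality test in the same 30 patients: one branch compares means, the other compares ranks and yields no mean difference. A later trial could not plan from the second without further work.

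The plan also leaves unused a baseline value that comes from the same sensor as the outcome, precedes allocation and is collected in both arms. If it predicts the outcome, adjusting for it narrows the interval at no data cost.

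**Working it through.** **Inputs.** From the documents: 15 per arm (section 10.1). No alpha, power, SD, effect size or correlation is given, so there is no planned figure to reproduce. Assumed: two-sided 5%, no losses, equal SDs, and a within-arm correlation r between baseline cardiac index and outcome of 0, 0.3, 0.5 or 0.7.

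**Unadjusted interval.** Half-width = t(0.975; 28) × SD × √(2/15) = 2.048 × 0.365 × SD = 0.748 SD. At an assumed SD of 15/25/35 percentage points this is 11.2/18.7/26.2 points.

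**Adjusted interval, same r in both arms.** Variance factor = (1 − r²)(1 + 1/26), with 27 degrees of freedom. For r = 0.5: 0.75 × 1.038 = 0.78. Width ratio = (2.052/2.048) × √0.779 = 0.884. Power is from the noncentral t at an assumed true difference of 0.8 SD.

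| | Variance factor | Width | Half-width at SD 25 | Power |
|---|---|---|---|---|
| Unadjusted | 1 | reference | 18.7 | 56% |
| r = 0 | 1.04 | +2% | 19.1 | 55% |
| r = 0.3 | 0.95 | −3% | 18.2 | 58% |
| r = 0.5 | 0.78 | −12% | 16.5 | 67% |
| r = 0.7 | 0.53 | −27% | 13.6 | 83% |

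Simulation (100,000 trials per setting, normal data) gave variance factors of 1.039 and 0.947/0.780/0.531, in agreement.

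**Link weaker in the GDT arm.** The same formula applies with the average slope in place of r: 0.75r if the link is half as strong under GDT, 0.5r if it exists only in the control arm. Simulated results at control-arm r = 0.3/0.5/0.7:
- Half-strength in GDT: variance 0.99/0.89/0.75; width −1/−5/−13%; power 57/61/68%.
- Control arm only: variance 1.02/0.98/0.92; width +1/−1/−5%; power about 55-56/57/60%.

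**Break-even on variance.** √(1 − 26/27) = 0.192 for a common r. With unequal slopes the control-arm r must reach 0.192/0.75 = 0.26 (half-strength) or 0.192/0.5 = 0.38 (control only).

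**Ceiling at 100%.** The outcome is bounded and may pile up. In three assumed ceiling settings the common-r narrowing fell from 3/12/27% to about 1-2/8-10/18-24%. Four other assumed settings gave about 1-2/5-10/13-22%. In a separate check of 15 settings (normal outcome clipped to 0-100; 16-37% of control and 37-84% of GDT patients at 100%), both the adjusted and the unadjusted interval covered 92.5-95.1% and never differed by more than 0.2 points. The ceiling reduces the gain but does not favour the unadjusted interval on coverage.

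**Chance imbalance.** The SD of the baseline mean difference is √(2/15) = 0.365 SD, so an imbalance of 0.5 SD or more occurs in about 17% of such trials. In those, with common r = 0.3/0.5/0.7, the unadjusted interval covers 0.931/0.885/0.824 and the adjusted one about 0.95. Over all trials both cover 95%.

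**The case against.** The strongest reply is that the unadjusted comparison is valid under randomisation and that every correlation above is assumed. The link may well be weak. The step 12 reading precedes lateral positioning and alveolar recruitment, and also "Begin unipulmonar ventilation" (step 17), "Epidural bolus of 5-7 ml of bupivacaine 0.1% plus fentanyl 5 mcg/ml" (step 18) and "START OF SURGERY" (step 19). Arm B is then reassessed every 10 minutes towards a cardiac index target. This stands, and it limits what can be claimed for the covariate.

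The t test is also not the only comparator. If the outcome piles up at 100%, section 10.2 would probably lead to Mann-Whitney. In one assumed setting (21% of control and 66% of GDT patients at the ceiling, r = 0.3), Mann-Whitney had 83% power against 79-82% for the adjusted model. A power gain over the plan as written is therefore not shown at weak correlation. The argument for an estimate with an interval does not depend on power.

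Three stronger readings are tempting, and the documents do not support them:
- *The planned test is biased.* It is not. The lower coverage under chance imbalance is conditional, arises with any prognostic covariate, and averages out to 95%.
- *The phrase about necessity leaves the choice of test undefined.* Read with the Kolmogorov-Smirnov sentence that opens section 10.2, it naturally means non-normal data. The rule can be read; the difficulty is that the data choose the quantity reported.
- *Nothing is quantified.* Per-arm summaries are planned. What is missing is the between-arm difference and its interval.

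**Conclusion.** The point holds as an improvement in precision and interpretability. The firmer half needs no assumption about correlation: the plan should name one between-arm estimate with an interval, fixed in advance, because the aim is to quantify and because 15 per arm leaves about ±0.75 SD of uncertainty that a p-value would hide.

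The covariate half is worth having because it is cheap, but its size is uncertain. The 3/12/27% narrowing rests on unbounded normal data, equal SDs and a common slope. It shrinks when many patients reach 100%, and is nil or slightly negative if the link is weak or largely confined to the control arm. The documents cannot say which case applies.

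A rule to adjust only if the expected correlation exceeds some break-even value would not help. Without prior data the investigators could not apply it, the threshold changes if the slopes differ by arm, and the primary analysis would again be conditional.

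**What to change.** In section 10.2, pre-specify one primary analysis in the ITT population:
- A linear model of the percentage of intraoperative time with cardiac index at or above 2.2 l/min/m² on arm and the step 12 baseline cardiac index.
- Report the adjusted mean difference, GDT minus conventional, with its 95% confidence interval (27 degrees of freedom) and the p-value from the same model, whatever the normality test shows.
- If a baseline value is missing, substitute the mean of all baseline values, so that no randomised patient leaves the model.
- As sensitivity analyses, report the unadjusted difference with its 95% interval, and Mann-Whitney.
- State the number of patients at 100% in each arm.

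The cost is a few sentences and one degree of freedom, with no new data and no change to patient care. If baseline cardiac index proves unrelated to the outcome, the price is about 4% more variance, a 2% wider interval, and 55% instead of 56% power at the assumed 0.8 SD difference.
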